#### 9.4.4. Summary of all Dense PK Serum Concentrations (Dense PK Subset)

Similar to the trough concentrations, summary of all serum concentrations of the Dense PK Subset measured in central lab (including the trough concentrations for the dense PK sampling period measured at central lab) will be done by analyte, whole population, age

category, treatment schedule (Q3W/Q4W) and by dosing regimen combining all dose levels. An additional summary will include the split by dose level for the last dose before sampling for dense PK, as presented above with 3 dose ranges (0.2-<0.4, 0.4-<0.6, 0.6-0.8 g/kg). For the summaries based on dosing bins, results for subjects with changes to dose level will be combined after dose adjustment based on dose history. Dose history will include the starting dose level and the adjusted dose level as well as the time of adjustment. If the dose adjustment was done close to the measurement of  $C_{ss}$  the resulting concentration may be excluded from the summary due to insufficient time to reach steady state at the adjusted dose level.

Nominal time points will be used for all summary statistics of PK concentrations. Summaries by age categories (based on the availability of pediatric subjects) will include the Dense PK Subset data for total IgG, IgG subclasses, and antigen-specific IgG. Data will be presented in separate table for each analyte.

Summary statistics will not be presented if 50% or more of the actual values for the Dense PK Subset at any time point are BLQ or missing or if less than 3 values are available. The reporting will be limited to median value for n=1 and to median, min and max values for  $1 < n \le 2$ .

All total IgG concentrations measured in the Dense PK Subset will also be presented as change from "baseline" concentrations with "baseline" defined in this case as a predose concentration before the start of dense PK sampling period. Change from baseline total IgG concentrations will be used in an additional PK analysis. (This definition of this "baseline" concentration will be indicated in appropriate tables, listings, and figures when relevant).

AUC 0-t /D	AUC 0-t normalized by dose level
AUC tau	Area under the serum concentration-time curve from time of dosing (infusion 7(Q3W) or 5 (Q4W)) to the end of dosing interval
AUC tau /D	AUCtau normalized by dose level
MRT	Mean residence time
Cavg	Average serum concentration over the dosing interval following infusion 7 (Q3W) or 5 (Q4W) calculated by dividing AUC tau over dosing interval (tau)
Css	Steady-state trough concentrations measured prior to infusion 7 (Q3W)/ 5 (Q4W) dosing interval
C ss /D	Steady-state trough concentrations measured prior to infusion 7 (Q3W)/ 5 (Q4W) dosing interval normalized by dose level
% Fluctuation	% fluctuation is computed as $100^{(C_{max}-C_{min})/C_{avg}}$ , where Cmin and C max measured over dosing interval following infusion 7 (Q3W)/ 5 (Q4W) dosing interval
CLss	An estimate of the total body clearance = Dose/AUCtau
Vss	Volume of distribution at steady-state
AUC 0-inf	Area under the concentration-time curve from time of dosing (infusion 7(Q3W)/ 5 (Q4W) extrapolated to infinity
AUC 0-inf /D	AUC 0-inf normalized by dose level
t 1/2	Serum terminal elimination half-life (time to reduce concentration by half during the terminal phase of the profile)
λz	terminal elimination rate constant

Clast	Last measured quantifiable concentration
tlast	Time point for the last measured quantifiable concentration

The noncompartmental analysis will be performed using an appropriate software solution. For the derivation of the PK parameters, the sampling time of pre-dose samples relative to dosing will be treated as time zero, using days as time units.

The PK parameters will be estimated as follows:

- The apparent Cmax and the corresponding tmax will be read directly from the concentrationtime plot of the observed data (not predicted data by the software);
- AUCs will be calculated using the linear/log trapezoidal rule.
- The terminal elimination rate constant ( $\lambda_z$ ) will be generally determined by log-linear regression obtained using the 3 last quantifiable concentrations and will not include Cmax. The adjusted square of the correlation coefficient (Rsquare adjusted) for the goodness of fit of the regression line through the data points must be at least 0.8500 for the  $\lambda_z$  value to be considered adequately reliable.

For sparse PK sampling for age category 2-5 years the 2 time points within the expected terminal phase time window may be used for calculation of  $\lambda z$ . The resulting data will be flagged as "sparse data" and will not be summarized.

- $t_{1/2}$  is calculated by the software as  $ln2/\lambda_z$ .
- If the time interval between the lower and upper time points used for the regression spans less than the derived half-life itself then  $\lambda_z$  and the associated  $t_{1/2}$  will be flagged as "calculation interval shorter than resulting elimination half-life". Summaries for the elimination parameters will be duplicated with all parameters available as well as flagged parameters excluded.
- The AUC from 0 to infinity is calculated by the program as: AUCinf = AUClast + AUClast-inf where last is the sampling time point of the last measurable concentration (tlast). AUClast-inf is calculated by the program as: Clast/ $\lambda_z$ , where Clast is the observed concentration at time tlast and  $\lambda_z$  is the elimination rate constant during the apparent terminal elimination phase; all AUCinf will be presented in the listings of PK parameters.
- Secondary PK parameters such as Rsquare adjusted, interval for  $\lambda_z$  calculation, number of points excluding Cmax to calculate  $\lambda_z$ , AUCextrap% will be listed separately for each subject.
- The AUC extrapolation to infinity must be ≤25% of the total area for AUCinf to be considered reliable.
- For subjects with PK parameter which do not meet acceptance criteria (i.e., Rsquare adjusted <0.8500, interval for  $\lambda_z$  calculation shorter than t1/2, number of points excluding

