- A subject diary (paper) will be dispensed.
- Health-related quality-of-life assessment will be performed. •
- Concomitant medications (including prohibited treatments) will be recorded. The content of the subjects' diaries will be reviewed and the type of concomitant medication, dose/schedule, duration, and the indication the concomitant medication was given for will be documented.
- Adverse events will be recorded. The content of the subjects' diaries will be reviewed and AEs will be documented.
- BT595 will be infused intravenously.

Pharmacokinetic Sampling (From Week 18 [3-Week Schedule] or From Week 16 [4-Week Schedule])

Serial sampling for PK analysis of total IgGs, IgG subclasses 1-4, and IgG specific antibody levels (anti-pneumococcal capsular polysaccharide, anti-hemophilus influenzae type B, anti-measles, anti-tetanus, anti-cytomegalovirus, and anti-HBs/hepatitis B) will be made at estimated steady-state after the 7th infusion of the 3-week schedule (Week 18) or after the 5th infusion of the 4-week schedule (Week 16). *The number of blood draws (and the amount of blood per sample) will be dependent on the subject's age category.*

For adult subjects (18-75 years, inclusive) and pediatric subjects (6-17 years, inclusive), samples will be taken at a fixed series of time points. Note: samples for IgG specific antibody levels will be taken from pediatric subjects aged 12 through 17 years only. Samples for all analytes will be taken as 1 aliquot. Subjects (6-75 years, inclusive) will have 8 or 9 PK blood samples taken (according to treatment schedule):

- 10 to 30 minutes before the infusion (note: this sample is the same sample as that taken for the trough levels of IgG subclasses 1-4 and IgG specific antibody levels before the 7th/5th infusion of the 3-week/4 week-schedule, respectively.)
- 10 to 30 minutes postinfusion (end of infusion sample)
- 4 hours (±1 hour) postinfusion
- 24 hours (±1 hour) postinfusion
- 4 days (±1 day) postinfusion
- 7 days (±1 day) postinfusion
- 14 days (±1 day) postinfusion
- 21 days (±1 day) postinfusion for trough IgG levels for all subjects (6-75 years, inclusive) both, in the 3-week treatment schedule and in the 4-week treatment schedule. This sample must be taken before the next infusion of BT595 for subjects in the 3-week treatment schedule.

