#### 3.3. BRIEF DESCRIPTION

Study 991 is a Phase III pivotal, open-label, prospective, uncontrolled, multicenter study investigating clinical efficacy, safety, and PK properties of the human normal immunoglobulin BT595 for intravenous (iv) administration as replacement therapy in subjects with PID.

The study is planned to be conducted in about 25 sites in Europe (Germany, Spain, United Kingdom, Hungary and Russia) and in the United States.

The study population includes male and female subjects aged 2 through 75 years with PID. For those countries where local regulations permit enrolment of adult subjects only, subject recruitment is restricted to those who are 18 through 75 years.

About 70 subjects will be enrolled to ensure data are available for at least 50 evaluable subjects. Amongst those subjects at least 20 subjects are to be adults (17 resp. 18 to <76 years,) and at least 20 subjects are to be pediatric (i.e., young children [2 to <6 years], children [6 to <12 years] or adolescents [12 to <17 resp. <18 years]). The age distribution represents the PID patient population.

According to FDA advice from January 12, 2017 for Pediatric Study Plan, age groups are defined as stated in the FDA 2016 guideline for pediatric study plans differently for the US: The age group of adolescents for the US is restricted to 12 to <17 years and therefore only subjects 2 to <17 years can be enrolled into the group of pediatric subjects.

A DSMB is to be established in this study to monitor the safety data. At least 10 adult subjects (18 to <76 years) who have received at least 2 BT595 infusions will be reviewed by the DSMB before any pediatric subjects are enrolled to the study. The DSMB reviews the safety data and provides recommendations on the suitability of the enrolment of pediatric subjects in the study depending on the assessment of possible safety concerns. However, the final decision to enroll/not enroll pediatric subjects is the responsibility of the sponsor.

BT595 is administered at 3- or 4-week intervals for a treatment period of approximately 12 months. The initial dose and dosage intervals are chosen to be consistent with the

subject's prestudy IVIg treatment and the initial dose and dosage interval are only changed if medically indicated. This change will be at the investigator's discretion.

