c Vital signs (pulse, blood pressure, respiratory rate) will be assessed within 30 minutes before each infusion, 15 to 30 minutes after the start of each infusion, 15 to 30 minutes after the end of each infusion, and 15 to 30 minutes after the start of any change in the infusion rate. The vital sign, temperature, will be recorded within 30 minutes before each infusion only.

d A pregnancy human chorionic gonadotropin test in serum will be taken for all female subjects ≥12 years of age or with presence of menstruation at screening. Urine pregnancy dipstick tests will be performed at all other study visits.

e Additional samples for safety laboratory assessments and total IgG will be taken at the end of the first BT595 infusion.

f Samples will be taken from subjects (6 to <76 years) at baseline and before the 7th/5th infusion of the 3-week/4-week schedule, respectively (i.e., this sample is the same sample as the predose sample for PK analysis).

 Samples will be taken from subjects (12 to <76 years) at baseline and before the 7th/5th infusion of the 3-week/4-week schedule, respectively (i.e., this sample is the same sample as the predose sample for PK analysis).

h At the 7th infusion (Week 18 [3-week schedule]) or 5th infusion (Week 16 [4-week schedule]), serum samples for the PK analysis of total IgG, IgG subclasses 1-4, and antigen specific IgG levels (anti-pneumococcal capsular polysaccharide, anti-hemophilus influenzae type B, anti-measles, anti-tetanus, anti-cytomegalovirus, and anti-HBs/hepatitis B) will be drawn from subjects (6 to <76 years for total IgG and IgG subclasses 1-4; 12 to <76 years for antigen specific IgG levels) at the following time points: predose (i.e., 10 to 30 minutes before the infusion), 10 to 30 minutes postinfusion (end of infusion), 4 and 24 hours postinfusion; and 4, 7, 14, 21 days (for the 3-week and the 4-week treatment schedule), and 28 days postinfusion (4-week schedule only). For pediatric subjects (2 to <6 years),

sparse sampling for PK analysis of total IgG only may be performed at flexible time points within specified time windows after the end of the infusion (note: these samples are optional).

Solest AG Protocol 99

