#### 9.6.5. Figures for PK Parameters

PK parameters will be presented on box plots for total IgG, 4 IgG subclasses, and 6 different antigen-specific IgG for each PK parameter individually ( $C_{max}/D$ , AUCtau/D and AUC0-inf/D, and t1/2z). Data will be reported separately for each dosing interval (Q3W and Q4W) and age category (FDA and EMA separately).

Box plots comparing PK parameters ( $C_{max}$ ,  $T_{max}$ , AUCtau, AUC0-inf,  $t_{1/2z}$ ) from complete and "in silico" reduced data sets will be presented by dosing schedule pooling together all subjects (6-75 years) and all dose levels.

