#### 9.8. EXPLORATORY COMPARISON OF STEADY-STATE PK PARAMETERS FOR TOTAL IGG, IGG SUBCLASSES AND SPECIFIC IGGS BETWEEN AGE CATEGORIES

Exploratory comparison of  $CL_{ss}$ , not dose-normalized and dose-normalized,  $C_{max}/D$ ,  $AUC_{tau}/D$  and if available  $AUC_{0-inf}/D$  using Dense PK Subset and  $C_{ss}$  and  $C_{ss}/D$  separately using the PK Trough set and the Specific IgG Trough PK set for the Q3W schedule and the 5th infusion for the Q4W schedule between age categories will be performed for total IgG, IgG subclasses and antigen specific IgGs by ANOVA approach as described above. Only subgroups with at least n=3 subjects will be retained for the comparison test.

Dense PK Subset will be used for the comparison of PK parameters. The PK Trough set and Specific IgG Trough PK set will be used for comparison of trough concentrations at steady state.

Log-transformed parameters for total IgG, IgG subclasses and specific IgGs will be compared separately by infusion schedule between age categories.

The same model will be repeated for dose normalized trough concentration and CLss.

The following contrasts will be explored:

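### AUC0-inf/D taken from the steady-state profile includes carry-over from earlier infusions, so it is not an exposure per dose and can distort the exploratory age comparison

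*SAP*

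**What the plan says.** **Sampling.** Protocol 7.1 places the dense PK profile at "estimated steady-state after the 7th infusion of the 3-week schedule (Week 18) or after the 5th infusion of the 4-week schedule (Week 16".

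**Derivation.** SAP 9.5.1 defines AUC0-inf as "Area under the concentration-time curve from time of dosing (infusion 7(Q3W)/ 5 (Q4W) extrapolated to infinity". It is computed as the area to the last measurable concentration plus Clast/λz, with λz "obtained using the 3 last quantifiable concentrations". A dose-normalised version, AUC0-inf/D, is listed as well. The same section defines CLss as "An estimate of the total body clearance = Dose/AUCtau".

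**Use.**
- SAP 9.5.2 summarises AUC0-inf/D by age category and dose level.
- SAP 9.6.5 puts it in box plots with Cmax/D, AUCtau/D and half-life: "Data will be reported separately for each dosing interval (Q3W and Q4W) and age category (FDA and EMA separately".
- SAP 9.8 compares age categories by ANOVA: "Log-transformed parameters for total IgG, IgG subclasses and specific IgGs will be compared separately by infusion schedule between age categories". AUC0-inf/D enters there only where it can be obtained, beside CLss, Cmax/D and AUCtau/D.
- SAP 9.9.1 compares it between full and reduced sampling sets.

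**Safeguards.** SAP 9.5.1 treats AUCinf as reliable only if at most 25% of it is extrapolated. It also flags elimination parameters when the regression span is shorter than the half-life. Flagged values may still enter summaries and tests, as a matter of judgement. Every parameter is also derived a second time after subtracting the pre-dose concentration. Sections 9.6.5 and 9.8 do not say which of the two sets they use.

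Neither document states that the uncorrected AUC0-inf contains drug from earlier infusions.

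**The concern.** At steady state, the area over one dosing interval equals the total area that one dose would produce alone. The SAP relies on this when it obtains clearance from AUCtau. Following the same curve to infinity adds the remains of all earlier infusions, yet the result is divided by a single dose. AUCtau/D and AUC0-inf/D then stand side by side as dose-normalised exposure, although they estimate different quantities.

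The age comparison is where this matters. It is meant to show whether children and adults reach similar exposure for a given dose. The excess in AUC0-inf/D depends on half-life, so a difference in half-life between age groups can be read as a difference in exposure.

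**Working it through.** The documents give no figure for AUC0-inf or its bias, so there is none to reproduce.

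**Inputs from the documents.** τ = 21 or 28 days (SAP 3.3). The last three nominal samples are at 7, 14, 21 days or 14, 21, 28 days (SAP 3.8 flowchart), a span of 14 days. CLss = Dose/AUCtau and the 25% limit come from SAP 9.5.1.

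**Assumptions.** Half-life 14 to 35 days; linear one-compartment kinetics; true steady state; no endogenous IgG.

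**Step 1: size of the carry-over.** With λ = ln2/t½, the steady-state curve is C(t) = (D/V)·exp(−λt)/(1 − exp(−λτ)). Hence:
- AUCtau/D = 1/CL
- AUC0-inf/D = (1/CL)/(1 − exp(−λτ))
- inflation factor = 1/(1 − exp(−λτ))
- extrapolated share of AUC0-inf = exp(−λτ)

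| Assumed t½ (days) | 3-week: factor | 3-week: extrapolated | 4-week: factor | 4-week: extrapolated |
|---|---|---|---|---|
| 14 | 1.55 | 35.4% | 1.33 | 25.0% |
| 21 | 2.00 | 50.0% | 1.66 | 39.7% |
| 28 | 2.47 | 59.5% | 2.00 | 50.0% |
| 35 | 2.94 | 66.0% | 2.35 | 57.4% |

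**Step 2: check on the SAP's own method.** A noncompartmental analysis was run on simulated biexponential steady-state profiles at the SAP sampling times, with the linear/log trapezoidal rule and the last three points for λz. AUC0-inf came out at 1.51 to 2.85 times (3-week) and 1.32 to 2.32 times (4-week) the true single-dose exposure for 14 to 35 days. AUCtau was within 0.5% of it throughout.

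**Step 3: the flags.** exp(−λτ) ≤ 0.25 requires t½ ≤ τ/2, that is 10.5 days (3-week) or 14 days (4-week). Only the 14-day, 4-week cell in the table meets the limit, and it is still inflated 1.33-fold. The 14-day regression span also flags any half-life above 14 days.

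**Step 4: the change-from-baseline set.** Subtracting a constant pre-dose value treats a decaying residue as flat. In the same simulation AUC0-inf fell to 0.24 to 0.51 (3-week) and 0.30 to 0.60 (4-week) of the true single-dose exposure. Only 10% to 21% of it was extrapolated, so these values can pass the 25% limit.

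**Step 5: age contrasts.** For equal volume and half-lives of 28 against 21 days, the AUCtau/D ratio is 28/21 = 1.33. The AUC0-inf/D ratio is 1.333 × 2.467/2.000 = 1.64 (3-week) or 1.333 × 2.000/1.658 = 1.61 (4-week). Other assumed combinations, against a reference half-life of 30 days:

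| Clearance, volume vs reference | AUCtau/D ratio | AUC0-inf/D ratio, 3-week / 4-week | Effect |
|---|---|---|---|
| +25%, same | 0.80 | 0.68 / 0.69 | exaggerated |
| +25%, +25% (equal half-life) | 0.80 | 0.80 / 0.80 | unchanged |
| +25%, +50% | 0.80 | 0.93 / 0.91 | attenuated |
| same, +25% | 1.00 | 1.20 / 1.18 | spurious |

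**The case against.** The strongest reply is that this parameter is already hedged. The age comparison is exploratory and uses AUC0-inf/D only where it can be obtained. The protocol (10.10) derives AUC0-inf only if the data allow. AUCtau/D and CLss are analysed beside it. For total IgG, contrasts involving ages 2 to under 6 are limited to trough levels. Step 3 shows that the flags would catch nearly all uncorrected values over the assumed half-lives, so the larger factors belong to values that the SAP itself calls unreliable. The protocol lists AUC0-inf among its PK parameters, so a footnote might be enough.

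Much of this stands, and it limits the weight of the point. It does not remove it. The flags test how much of the area is extrapolated and how well λz is supported; they do not test for carry-over. Use of flagged values is left to judgement rather than excluded by rule. The pre-dose subtraction replaces an upward error with a downward one.

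The objection holds fully for SAP 9.9.1. There the full and reduced sets come from the same subject, with the same dose and the same carry-over in both. The question is sensitivity to sampling, so this argument gives no reason to remove AUC0-inf from that section.

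**Conclusion.** The uncorrected AUC0-inf/D is not an exposure per dose. It exceeds AUCtau/D by a factor of about 1.5 to 2.9 (3-week) or 1.3 to 2.3 (4-week), given the assumed half-lives and linear kinetics at steady state. It should not serve as an age-comparison measure, because it can show a difference of 18% to 20% where clearance is identical.

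Two stronger readings are tempting and are not supported. A reader might infer that AUC0-inf/D always exaggerates age differences. The direction depends on how clearance and volume differ by age, which the documents do not give, and with equal half-lives the factor cancels on the log scale. A reader might also infer that AUC0-inf/D is overstated in every planned analysis. In the change-from-baseline set it is understated.

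The consequence is confined to exploratory PK outputs. No efficacy conclusion depends on it.

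**What to change.** - Remove AUC0-inf/D from the age-category box plots in SAP 9.6.5. AUCtau/D is already plotted there.
- Remove it from the age comparison in SAP 9.8. AUCtau/D and CLss are already compared there.
- Where AUC0-inf or AUC0-inf/D is kept in listings, in the 9.5.2 summaries or in the 9.9 sampling comparison, label the uncorrected value as including carry-over from earlier infusions and not a single-dose exposure. Note beside the change-from-baseline version that the subtraction does not recover single-dose exposure either.

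The cost is the loss of a few planned exploratory outputs and the addition of some footnotes. No new derivation or data are needed. AUC0-inf can still be derived and listed as the protocol foresees.

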#### Statistical Analysis Plan

#### Version Final 2.0

Cmax to calculate  $\lambda_z < 3$ ),  $\lambda_z$ ,  $t_{1/2}$ , AUCinf will be flagged based on the specific criteria in the individual data listings.

- CLss is calculated by program as (Dose/AUCtau).
- For subjects with unreliable AUCinf (because of extrapolation >25%), AUCinf will be reported, but flagged in the individual data.

All PK parameters will be estimated both by baseline corrected and baseline uncorrected.

Flagged PK parameters will only be included in summarization and statistical analyses after careful consideration.

The PK parameters derivation will be based on data availability for analytes total IgG, or total IgG and IgG subclasses, and antigen-specific IgG by different age categories. Data for different analytes will be summarized in separate tables.

#### 9.5.2. Summary of PK Parameters

Individual PK parameters for original concentration values and for change from "baseline" from complete and reduced data sets will be all listed for each subject when available. PK parameters for original concentration values and for change from baseline will be summarized similarly to the serum concentrations based on data availability (see Section 9.3) for different age categories, by age category and dose levels, individually for the two dosing regimen (Q3W and Q4W), as described in Section 9.4.1 for trough levels. Briefly, PK parameters will be summarized by analyte, and age category combining all dose levels. Additional summaries will include the split by dose level for the latest dose before sampling, as presented above with 3 dose ranges (0.2-<0.4, 0.4-<0.6, 0.6-0.8 g/kg). Comparison between complete PK parameters derived from the full dataset and the "in silico" reduced datasets is further described in Section 9.9.

Variable	Summarized with:
AUC 0-t , AUC 0-t /D, AUC tau , AUC tau /D, AUC 0-inf , AUC 0- inf /D, C max , C avg , C ss , , CL ss , C max /D, C ss /D, C trough , C last , MRT, %Fluctuation, V ss	n, arithmetic mean, SD, CV%, minimum, median, maximum, geometric mean, and geometric CV%
$t_{1/2}$ , and $\lambda_z$	n, arithmetic mean, SD, CV%, minimum, median, and maximum
t max (actual time), t last	n, minimum,Q1, median, Q3, and maximum

The following descriptive statistics will be provided:

Note: CV% = SD/mean in %.

%BLQ = 100 \* (total number of subjects who have BLQ values/total number of subjects within each cohort at each time point)

The following conventions will be used for the presentation of the descriptive statistics of PK parameters and of serum concentrations:

PK Reporting Precision

Statistics	Degree of Precision
Minimum, Maximum	3 significant digits or as needed based on actual measured values (for example PK concentrations)
Mean (arithmetic and geometric), Median	4 significant digits or as needed based on actual measured values (for example PK concentrations)
Standard deviation	5 significant digits or as needed based on actual measured values (for example PK concentrations)
CV% and Geometric CV%	1 decimal point or as needed based on actual measured values (for example PK concentrations)

